Safety: Safety analyses will be conducted on the Safety analysis set. Safety parameters that will be assessed include: adverse events, clinical laboratory parameters, vital signs, electrocardiogram parameters, and physical examination. The parameters will be listed and summarized using standard descriptive statistics.

Pharmacokinetics/Pharmacodynamics: Plasma PRCL-02 PK parameters after multiple dose administration will be calculated using noncompartmental methods. Pharmacokinetic parameters

will be summarized by dose level using descriptive statistics. Mean and individual PRCL-02 plasma concentration-time curves will be represented graphically.

The PK/PD relationship between PRCL-02 exposure and PD efficacy and/or safety measures may be explored.

2. Schedule of Activities

Table PRCL 1 **Schedule of Activities**

Procedure	Screening ^a	1	2	3	4	5	6	7	8	9	FU	EoS ^b
Visit #												
Study Days	-28 to -1	1	8	15	29	57	85	99	113	127		141
Window Period (Days)		±2	±2	±2	±2	±2	±2	±2	±2	±2		±2
Week	-	-	1	2	4	8	12	14	16	18		20
Informed consent	X											
Demographics	X											
Medical history	X											
Inclusion and exclusion criteria	X	X										
Pregnancy test (♀) ^c	X	X	X	X	X	X	X	X	X	X		
Serum FSH (PMP ♀)	X											
QuantiFERON TB Test ^d	X											
HIV/hepatitis screen	X											
Randomization		X										
Study drug dispensing ^e		X	X	X	X	X						
Study drug accountability			X	X	X	X	X					X if ET
Safety Evaluations												
Physical examination ^f	X	X	X	X	X	X	X					X
Height/weight ^g	X	X	X	X	X	X	X					X
Vital signs (pulse and BP) ^h	X	X	X	X	X	X	X	X	X	X		X
12-lead ECG ⁱ	X	X	X	X	X	X	X					X
Clinical laboratory tests ^j	X	X	X	X	X	X	X					X
AE monitoring	X	X	X	X	X	X	X	X	X	X		X
Concomitant medications	X	X	X	X	X	X	X	X	X	X		X
Efficacy and Other Evaluations												
PASI	X	X	X	X	X	X	X	X	X	X		X
sPGA	X	X	X	X	X	X	X	X	X	X		X
PK sampling ^k			X	X	X	X	X	X	X	X		X
Plasma sample collection for PGx assessments		X										

Abbreviations: AE = adverse event; BP = blood pressure; ECG = electrocardiogram; EoS = end-of-study; FSH = follicle stimulating hormone; FU = Follow-up; HIV = human immunodeficiency virus; PGx = pharmacogenomics; PK = pharmacokinetics; PMP = postmenopausal; S = screening; sPGA = static physician's global assessment; TB = tuberculosis.

- ^a Randomization will be within 28 days following the screening visit.
- ^b In the event of early or premature discontinuation, a patient should undergo all activities per the EoS visit.

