2.7. Handling of Dropouts and Missing Data

Dates

Imputation of missing or partial dates is not expected, but if a complete date is required for calculations, the following algorithms will be applied:

- For the start date:
 - If year, month, and day are missing then use the minimum of the patient's first visit date or the consent date.
 - If either only month or month and day are missing then use January 1.
 - If only day is missing, impute the first day of the month.

- For the end date:
 - If year, month, and day are missing then use the patient's last visit date.
 - If either only month or month and day are missing then use December 31.
 - If only day is missing then use the last day of the month.
 - Do not expand the record past the patient's last visit.

The original missing or partial date, the imputed complete date, and the indicator variable that indicates which dates were imputed will be retained in the database.

PASI and sPGA Response

Patients whose response to treatment cannot be determined due to missing data (including early withdrawal) will be considered non-responders in the analyses.

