5.3. Exploratory Analyses

The percentage of patients with a $\geq 90\%$ improvement from baseline in PASI (PASI 90) at 12 weeks will be analyzed similarly to PASI 75. PASI 75 and PASI 90 will be summarized at each scheduled visit.

Observed values of the PASI score and subscores, the sPGA score, and the change and percent change from baseline to each scheduled visit will be summarized using descriptive statistics and the treatment groups compared using analysis of variance methods.

The quantitative secondary efficacy endpoints will be assessed by analyzing the change from baseline to the 12-week time point using PROC MIXED to model the difference in the Week 12 change from baseline score between treatment groups and to handle missing assessments. The change from baseline to each scheduled post-baseline visit will be estimated using repeated measures mixed models assuming data are missing at random, with covariates for baseline and visit. The lower 95% confidence limit of the difference in mean scores at Week 12 (PRCL minus Placebo) will be estimated from the mixed model. The effects of baseline scores and treatment will be allowed to vary across visits. The following example SAS code will be used, for assessments at Weeks 1, 2, 4, 8, and 12. For patients who withdraw prior to Week 12, data from the early termination visit will be used as the next visit's assessment; for example, if a patient's last scheduled assessment is at Week 4, the early termination data will be included in the analysis as Week 8.

```
proc mixed;
  class visit treatment patient;
  model endpoint=week*baseline week*treatment;
  repeated week / type=vc subject=patient;
  random patient;
run;
```

In addition, plots of each least squares mean (\pm standard error) for the scores by scheduled visit will be created

If the data appear non-Normal or if a reasonable variance-covariance structure cannot be fit to the data, the treatment comparisons will be made using Wilcoxon Rank-Sum tests at each visit using the observed data.

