7. PHARMACOKINETIC/PHARMACODYNAMIC ANALYSES

Pre-dose samples are to be obtained at 1 week, 2 weeks, 4 weeks and 8 weeks after the first dose of study drug. On the last day of dosing (Day 85/Week 12), the following samples are to be collected: pre-dose and 1, 2, 4, 8, 24 (Day 86), 72 hr (Day 88), and 168 hr (1 week; Day 92) post dose. One sample should be taken at the EOS visit (at least 6 weeks after the last dose [Week 18]). One sample should be taken at the early termination visit, if applicable.

Pharmacokinetic parameters will be summarized by dose level using descriptive statistics. PK parameters such as the maximum concentration (C_{max,ss}), time of maximum concentration (T_{max,ss}), area under the concentration versus time curve within a dosing interval (AUC_{0- τ ,ss}), the first-order terminal elimination rate constant (λ_z), the terminal elimination half-life (t_{1/2}), apparent clearance (CL/F), and apparent volume of distribution (V_d/F) will be reported. Other parameters may be calculated as deemed appropriate. Mean and individual PRCL-02 plasma concentration-time curves will be represented graphically.

Note that for all PK parameters but T_{max}, summary statistics will include geometric mean and geometric CV%. T_{max} will be reported as median and range (minimum to maximum).

The PK/PD relationship of PRCL-02 with PD, efficacy, and/or safety measures may be explored.

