9. SCHEDULE OF ASSESSMENTS

Procedure	Screening									FU	EoS
Visit #	1	2	3	4	5	6	7	8	9	10	11
Study Days	-28 to -1	1	8	15	29	57	85	99	113	127	141
Window Period (Days)		±2	±2	±2	±2	±2	±2	±2	±2	±2	±2
Week	-	-	1	2	4	8	12	14	16	18	20
Informed consent	X										
Demographics	X										
Medical history	X										
Inclusion and exclusion criteria	X	X									
Pregnancy test (♀)	X	X	X	X	X	X	X	X	X	X	
Serum FSH (PMP ♀)	X										
QuantiFERON TB Test		X									
HIV/hepatitis screen	X										
Randomization		X									
Study drug dispensing		X	X	X	X	X					
Study drug accountability			X	X	X	X	X				X if ET
Safety Evaluations											
Physical examination	X	X	X	X	X	X	X				X
Height/weight	X	X	X	X	X	X	X				X
Vital signs (pulse and BP)	X	X	X	X	X	X	X	X	X	X	X
12-lead ECG	X	X	X	X	X	X	X				X
Clinical laboratory tests	X	X	X	X	X	X	X				X
AE monitoring	X	X	X	X	X	X	X	X	X	X	X
Concomitant medications	X	X	X	X	X	X	X	X	X	X	X
Efficacy and Other Evaluations											
PASI	X	X	X	X	X	X	X	X	X	X	X
sPGA	X	X	X	X	X	X	X	X	X	X	X
PK sampling			X	X	X	X	X	X	X	X	X
Plasma sample collection for PGx assessments		X									

See protocol for footnotes.

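### In the exploratory mixed model of SAP 5.3, early-termination PASI and sPGA scores are labelled as the next visit whatever their actual day, so a Day 59 score can enter as the Week 12 value

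*SAP*

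**What the plan says.** SAP 5.3 compares the arms on change from baseline in the continuous scores with a repeated-measures mixed model "for assessments at Weeks 1, 2, 4, 8, and 12". The target is the Week 12 difference. Treatment effects may vary by visit, and missing assessments are handled under a missing-at-random assumption.

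For patients who withdraw before Week 12, "data from the early termination visit will be used as the next visit's assessment". The worked example counts from the last visit attended: "if a patient's last scheduled assessment is at Week 4, the early termination data will be included in the analysis as Week 8".

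Nothing elsewhere ties the label to a date. SAP 2.6 analyses by the nominal eCRF visit, without windows by study day. Footnote b of the schedule in Protocol Section 2 says "In the event of early or premature discontinuation, a patient should undergo all activities per the EoS visit". The EoS visit includes PASI and sPGA, and no time limit is set for an early-termination visit.

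Responder endpoints have their own rule in SAP 2.7: "Patients whose response to treatment cannot be determined due to missing data (including early withdrawal) will be considered non-responders in the analyses".

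**The concern.** The visit label depends only on which scheduled visit came last. The actual day of the early-termination score plays no part. The model fits a separate treatment effect for each week, so a relabelled score goes straight into the cell for its new week and into the least-squares-mean plot. When that week is Week 12, it enters the model's main estimate.

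The rule is also not needed to keep the patient in the analysis. A mixed model under missing at random uses incomplete profiles as they are. Moving an earlier score forward adds a form of carry-forward to a method chosen to avoid it.

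Response over time by PASI and sPGA is a stated exploratory objective (SAP 1.2). If the drug effect were still building, scores moved forward would understate Week 12 benefit. If a patient left for lack of effect and would have worsened, they would hide that. Which of these occurs depends on when and why patients leave each arm.

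**Working it through.** **Inputs**
- Scheduled days for Weeks 1, 2, 4, 8 and 12: Days 8, 15, 29, 57 and 85, each with a window of ±2 days (SAP Section 9; Protocol Table PRCL 1).
- 27 patients per arm and 10% drop-out (SAP 1.3).
- PASI trajectory and SD: not given in either document. Values used below are assumptions.

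**The plan's own figure.** The plan states no figure for this rule. Its one design figure is power of at least 80% for PASI 75. Exact enumeration of the one-sided Fisher test at 10% with 27 per arm, counting drop-outs as non-responders (7.5% × 0.9 = 6.75% against 37.5% × 0.9 = 33.75%), gives 84.2%. The figure is reproduced, and the rule examined here does not enter it.

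**Step 1: late placement.** Shift = scheduled day of the assigned visit − actual early-termination day.
- Week 8 on Day 57, termination on Day 59, entered as Week 12: 85 − 59 = 26 days.
- Termination the day after a nominal Week 8 visit: 85 − 58 = 27 days. After a nominal Week 4 visit: 57 − 30 = 27 days.
- Week 8 visit at the early edge of its window (Day 55), termination on Day 56: 85 − 56 = 29 days.

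**Step 2: early placement.** This needs a missed scheduled visit, and it needs the label to be counted from the last visit attended, as in the SAP's example.
- Last visit Week 4, Week 8 missed, termination on Day 82, entered as Week 8: 82 − 57 = 25 days early. Week 12 is left empty although a score exists 85 − 82 = 3 days from it.
- The same patient terminating on Day 84: 84 − 57 = 27 days early.
- Weeks 4 and 8 both missed, termination on Day 84, entered as Week 4: 84 − 29 = 55 days early.

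**Step 3: how many patients.**
- All planned drop-outs: 10% × 27 = 2.7 per arm. This is a ceiling at the planned rate.
- A misplaced score reaches Week 12 by late placement only if the patient leaves between Week 8 and Week 12. With drop-out uniform over Days 1 to 85 (assumption): 2.7 × 28/84 = 0.9 per arm, with an average shift of about 28/2 = 14 days.

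**Step 4: size on the raw Week 12 arm mean (assumptions only).** Effect = patients affected × points per patient / 27.
- 1 patient differing by 1 point: 1/27 = 0.04. 3 patients differing by 5 points: 15/27 = 0.56.
- Linear improvement of 12 points over 84 days, uniform drop-out: 12 × 14/84 = 2 points per patient, and 2 × 0.9/27 = 0.07.
- Same slope, all 2.7 drop-outs leaving on Day 59: 12 × 26/84 = 3.7 points per patient, and 3.7 × 2.7/27 = 0.37.

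The treatment difference moves by the difference between the two arms' shifts. These may partly cancel, or add if they have opposite signs.

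**Step 5: assignment by actual day.** Midpoints are (8+15)/2 = 11.5, (15+29)/2 = 22, (29+57)/2 = 43 and (57+85)/2 = 71. The Day 59 score goes to Week 8, 2 days off, and the Day 82 score to Week 12, 3 days off. The largest shift for termination up to Week 12 is 85 − 71 = 14 days.

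**The case against.** The rule is prespecified, has a worked example and can be programmed. It feeds an exploratory model, and SAP 5.3 also summarises observed values by visit. All of this stands, and it limits the weight of the point.

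The number of misplaced Week 12 scores is small. Patients lost to follow-up may have no early-termination visit, those without a Week 1 PASI are outside the ITT population, and those who leave after Week 12 are not concerned. A reader might take 3 of 27 per arm as the number with a wrong Week 12 score. The documents do not support that, because it counts every planned drop-out.

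Early placement is a narrow case. The Day 82 example falls one day outside the Week 12 window of Days 83 to 87. If the next visit is counted from the termination date, early placement does not arise. The SAP's example points to the last visit attended but does not address a missed visit.

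A reader might also see a contradiction in the Day 59 leaver being a PASI 75 non-responder yet having a Week 12 score in the model. That is not a defect in itself: a binary and a continuous endpoint can have different missing-data rules, and this patient would remain a non-responder under any change proposed here.

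The best objection concerns the remedy. A patient's last score before leaving may be the only record of worsening, and it helps to make missing at random plausible. Discarding it when the nearest visit already has a score trades one possible bias for another. This stands, and it is the reason to keep the current rule as a sensitivity analysis.

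**Conclusion.** The point holds as a minor, cheaply corrected weakness of the exploratory mixed model and its plots. Scores can be placed 27 days late on nominal visit days, or 29 with the window. On the SAP's literal example, they can also be placed early when a visit has been missed.

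Two stronger conclusions are not supported. First, a reader might infer that the primary endpoint is affected, because the misplaced score is called Week 12 and because SAP 5.3 refers to these measures as secondary. PASI 75 and the other responder analyses follow SAP 2.7, and SAP 1.2 lists PASI and sPGA over time as exploratory. Second, a reader might infer a known bias against or in favour of the drug. Without a PASI trajectory, an SD or reasons for leaving by arm, neither direction nor size can be derived. Under the assumed ranges the effect on an arm mean is about 0.04 to 0.56 PASI points. The uniform drop-out behind the estimate of about 1 patient per arm is also an assumption.

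**What to change.** Replace the early-termination rule in SAP 5.3 with:

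> The early-termination assessment is assigned to the scheduled visit nearest its actual study day (Week 2 from Day 12, Week 4 from Day 22, Week 8 from Day 43, Week 12 from Day 71). If that visit already has a scheduled score, the scheduled score is kept in the main model. Later visits are left missing and handled by the mixed model. The model is repeated with early-termination data entered as the visit after the last scheduled assessment, as a sensitivity analysis.

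The cost is a short SAP change, a small change to the derivation and one extra model run. The real downside is lost data in the main model. Early-termination scores from Days 30 to 42 after a Week 4 visit and Days 58 to 70 after a Week 8 visit drop out. By the same midpoints, so do those from Days 9 to 11 after Week 1 and Days 16 to 21 after Week 2. The sensitivity analysis keeps these scores in view, and any material disagreement between the two runs should be reported. The primary analysis and its power do not change.

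### The SAP's mixed-model code forces one common variance on all five visits; if the variance of change from baseline rises over time, the Week 12 standard error is too small and the early error bars are too wide.

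*SAP*

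**What the plan says.** SAP Section 5.3 models change from baseline with PROC MIXED and introduces the program with "The following example SAS code will be used, for assessments at Weeks 1, 2, 4, 8, and 12". The covariance is set by two statements, "repeated week / type=vc subject=patient" and "random patient". The mean model is flexible: "The effects of baseline scores and treatment will be allowed to vary across visits".

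Two outputs depend on the model's standard errors. One is the Week 12 inference: "The lower 95% confidence limit of the difference in mean scores at Week 12 (PRCL minus Placebo) will be estimated from the mixed model". The other is the set of "plots of each least squares mean", with standard-error bars, which "for the scores by scheduled visit will be created".

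The fallback reads: "if a reasonable variance-covariance structure cannot be fit to the data, the treatment comparisons will be made using Wilcoxon Rank-Sum tests". These tests use observed data at each visit. No other covariance structure is named and no criterion for a reasonable structure is given.

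**The concern.** In PROC MIXED, TYPE=VC on the REPEATED statement with no GROUP= option estimates a single residual variance. The random patient intercept adds a single between-patient variance. Their sum, the total variance, is the same at every visit. The plan thus lets treatment and baseline effects change from visit to visit but does not let the spread change.

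Change from baseline is an outcome for which a constant spread is doubtful. Shortly after the start, most patients are still close to their baseline score; by Week 12 the correlation with baseline may have weakened and responders may have separated from non-responders. If so, the model lends the smaller early variance to Week 12 and the larger late variance to Week 1. The Week 12 limit would then lie too close to the estimate, and the plotted bars would look too uncertain early and too certain late.

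**Working it through.** **The plan's own figures.** Neither document gives an SD, SE or power for the mixed model, so there is nothing to reproduce for this analysis. The only design figure is 27 patients per arm for at least 80% power on PASI 75 (SAP Section 1.3). It reproduces: exact one-sided Fisher power at 10% is 88.2% for 7.5% against 37.5%, and 84.2% when 10% drop out as non-responders (6.75% against 33.75%).

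**Formula.** Assume complete data, with treatment and baseline effects at every visit. The point estimate at each visit is then the same as from a separate ANCOVA at that visit, and the total variance estimated under compound symmetry is the average of the visit variances. Hence, at visit t,

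model SE / true SE = sqrt(mean of the five visit variances) / SD at visit t.

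With ratio r at Week 12, a nominal one-sided 95% limit covers approximately Φ(1.645 × r).

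**Inputs.** The five visits come from SAP Section 5.3. The visit SDs are assumptions. Only their relative sizes matter, so the formula holds for PASI or sPGA on any scale; no pattern specific to sPGA was examined.

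| Assumed SD at Weeks 1, 2, 4, 8, 12 | Mean variance | Ratio, Week 1 | Ratio, Week 12 | Coverage, Week 12 |
|---|---|---|---|---|
| 2, 3, 4.5, 6, 7 | 23.65 | sqrt(23.65/4) = 2.43 | sqrt(23.65/49) = 0.695 | 87% |
| 3, 4, 5, 6, 7 | 27.0 | sqrt(27/9) = 1.73 | sqrt(27/49) = 0.742 | 89% |
| 5, 5.5, 6, 6.5, 7 | 36.5 | sqrt(36.5/25) = 1.21 | sqrt(36.5/49) = 0.863 | 92% |
| equal at all visits | – | 1.00 | 1.00 | 95% |
| 3, 5, 6.5, 6, 5 (peak in the middle) | 27.45 | 1.75 | 1.05 | 96% |
| 6, 5.5, 5, 4.5, 4 (falling) | 25.5 | 0.84 | 1.26 | 98% |

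**Simulation.** The SAP model was fitted by REML to simulated trials of 3 × 27 patients, with correlation 0.75 between adjacent visits decaying with distance, 0% or 10% drop-out, and 2,500 trials per setting. `week` was taken as the class variable.

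| Assumed SDs | Ratio, Week 12 | Coverage, Week 12 |
|---|---|---|
| equal | 0.98–1.00 | 95% |
| 4 rising to 6 | 0.83–0.84 | 91% |
| 2 rising to 6 | 0.71 | 88% |
| 1.5 rising to 8 | 0.63–0.65 | 84–86% |
| 6 falling to 4 | 1.25–1.28 | 98% |

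The formula gives 0.84, 0.71, 0.64 and 1.26 for the four unequal patterns, so the two agree. Drop-out of 10% changed little.

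**Is rising variance plausible?** As an illustration, suppose the PASI variance is the same at every visit and its correlation with baseline falls as 0.9, 0.85, 0.75, 0.6, 0.5 (assumed). After baseline adjustment the variance is proportional to 1 − correlation²: 0.19, 0.2775, 0.4375, 0.64, 0.75, with mean 0.459. The ratios are sqrt(0.459/0.19) = 1.55 at Week 1 and sqrt(0.459/0.75) = 0.78 at Week 12. A constant correlation of 0.8 gives 1.00 at every visit.

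**With visit-specific variances.** With complete data this is a separate ANCOVA at each visit. In 10,000 simulated trials per setting the ratio was 1.00 (SD 2) and 1.01 (SD 6), and coverage was 95.2% and 95.6%.

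**The case against.** The strongest reply is that the direction of the error is not in the documents. No SD of change is reported at any visit, and equal, mid-peaking or falling SDs give no error, almost none at Week 12, or the opposite error. That stands. A reader might take the assumed 37.5% response as proof that variance grows, but that figure concerns the active arms at Week 12 only and says nothing about Week 1. A responder mixture would also suggest that variance differs by arm, which an unstructured matrix common to all arms does not address.

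Second, the code is labelled an example, SAP Section 2.1 calls for checking model assumptions, and the fallback may be read as allowing other structures before Wilcoxon. This stands in part. A reader might infer that one misfit of the printed structure sends the analysis straight to rank tests; the wording does not say so. But the SAP also says that the code will be used, it names no alternative structure, and Section 2.1 offers transformations or nonparametric methods, not another covariance. Compound symmetry normally converges, so a convergence failure is unlikely to prompt a change.

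Third, the analysis is exploratory (SAP Table 1; protocol Section 4). Section 5.3 does speak of quantitative secondary endpoints, but SAP Section 5.2 confines secondary analyses to safety and PK. No decision rule uses the Week 12 limit. Section 5.3 also calls for descriptive summaries and analysis of variance by visit, and Section 8 includes SDs, so the spread at each visit will be visible beside the model. All of this stands and limits the weight of the point.

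**Conclusion.** The point holds in conditional form. As printed, the code imposes equal variance and equal correlation across Weeks 1 to 12, and the Week 12 limit and the plotted bars inherit it. If the variance of change differs by visit, the standard errors are wrong. If it rises, which is plausible but undocumented, the Week 12 SE is 0.70 to 0.86 of its true value under the assumed SDs, with coverage of about 87% to 92% instead of 95% and Week 1 bars 1.2 to 2.4 times too wide. These sizes rest on the assumed SDs and on the complete-data formula, which the simulation supports for similar patterns.

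The documents do not support the stronger reading that the Week 12 limit is certain to be too narrow, or that the trial's main conclusion is at risk. Only the exploratory analyses of change in PASI and sPGA are affected; the primary Fisher test on PASI 75 is not.

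**What to change.** In SAP Section 5.3:

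- Use `repeated week / type=un subject=patient;`, drop the RANDOM statement and add `ddfm=kr` to the MODEL statement. Five visits give 5 × 6 / 2 = 15 covariance parameters, with 81 patients planned.
- List `week` in CLASS. The printed code lists `visit` there but uses `week` in MODEL and REPEATED. A REPEATED effect must be a class variable, so the program would not run as written.
- Pre-specify heterogeneous-variance structures to be tried in order if the unstructured matrix does not converge, for example TOEPH and then ARH(1). Other orders are acceptable, provided one is fixed in advance.
- State that these structures are tried before any covariance misfit leads to observed-case Wilcoxon tests, which would give up the missing-at-random handling of withdrawals that the model is meant to provide.

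The cost is a few words of code. If variance does rise, the distance from the Week 12 estimate to its limit grows by the inverse of the ratio: 1/0.863 = 1.16, 1/0.742 = 1.35 and 1/0.695 = 1.44, so about 16% to 44% under the assumed SDs. That extra width is uncertainty that the printed code would leave out.

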2. GENERAL STATISTICAL METHODOLOGY AND CONVENTIONS

2.1. General Considerations

All computations for statistical analyses will be performed using SAS® software, Version 9.4 or later. All SAS programs used in the production of statistical summary outputs will be validated with independent programming prior to finalization. In addition, all program outputs will be independently reviewed. The validation process will be used to confirm that all data manipulations and calculations were accurately done. Once validation is complete, a senior statistical reviewer will perform a final review of the documents to ensure the accuracy and consistency with this plan and consistency within tables. Upon

completion of validation and quality review procedures, all documentation will be collected and filed by the project statistician or designee.

Before implementation of parametric methods of analysis, the distribution of analysis variables will be examined to determine if model assumptions are satisfied. Transformations or nonparametric methods of analysis may be used if warranted. However, in some cases, nonparametric analysis may be the initially proposed method due to the expected distribution of response. Whenever alternative methods of analysis are required, the description of the new method along with the rationale for its use will be documented in the CSR.

The eCRF data for all patients will be provided in Standard Data Tabulation Model (SDTM) datasets. Data listings supplied as part of the CSR will be sorted by investigative site and patient identification number, and patients will be identified in the listings by the investigator number concatenated with the patient number.

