2.10. Adjustment for Covariates

Efficacy analyses will adjust for the baseline value of the endpoint where possible. Exploratory analyses may be performed that adjust for the strata used in the randomization.

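### Minor, cheap to fix: the SAP 5.3 fallback for continuous PASI and sPGA drops the missing-data handling and the baseline covariate because of distribution shape or covariance fit, so the exploratory Week 12 comparison can err either way if dropout is response-related and differs by arm

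*SAP*

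**What the plan says.** SAP 5.3 (Exploratory Analyses) gives the planned method for the quantitative scores. Change from baseline at each visit "will be estimated using repeated measures mixed models assuming data are missing at random, with covariates for baseline and visit". It states that the mixed model is used partly to handle missing assessments. For patients who withdraw before Week 12, "data from the early termination visit will be used as the next visit's assessment".

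The closing sentence of SAP 5.3 gives the fallback. The trigger is "If the data appear non-Normal or if a reasonable variance-covariance structure cannot be fit to the data". The action is that "the treatment comparisons will be made using Wilcoxon Rank-Sum tests at each visit using the observed data". No criterion is given for judging non-Normality.

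Three other sections bear on this:

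- SAP 2.10: "Efficacy analyses will adjust for the baseline value of the endpoint where possible".
- SAP 2.1: "Transformations or nonparametric methods of analysis may be used if warranted". Any alternative method and its rationale go into the study report.
- SAP 2.7: "Patients whose response to treatment cannot be determined due to missing data (including early withdrawal) will be considered non-responders". This rule is for PASI and sPGA response, not for the scores.

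Protocol 10.3.1 sets one-sided 10% tests and assumes that withdrawal is unrelated to the treatment effect. It allows supportive analyses of early withdrawal, but only for the primary endpoint.

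**The concern.** The planned model and the fallback answer different questions. The mixed model estimates the Week 12 difference for the ITT patients, using each patient's earlier visits and baseline to account for missing later ones. The Wilcoxon test at Week 12 has as its null hypothesis that the two arms have the same distribution among patients who have a Week 12 score. The two agree when the missing patients are like those who stay. They part when patients leave because they are not improving and one arm loses more of them.

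The direction depends on which arm loses more poor responders. More such leavers on placebo make placebo look better and hide a drug effect. More such leavers on drug make the drug look better and can create an apparent effect. A decision about distribution shape or covariance fit thus also changes the missing-data assumption, and no other section restores it. At stake is the reading of response over time, which is an exploratory objective.

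**Working it through.** **1. Inputs from the documents.** 27 per arm, 1:1:1 allocation and 10% dropout in each arm (SAP 1.3); one-sided 10% tests (protocol 10.3.1); visits at Weeks 1, 2, 4, 8 and 12 (SAP 5.3); PASI at least 12 at entry (protocol 6.1).

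**2. The plan's own figure.** SAP 1.3 claims at least 80% power for PASI 75. Counting dropouts as non-responders, the rates are 0.9 × 7.5% = 6.75% and 0.9 × 37.5% = 33.75%. Exact enumeration of the one-sided Fisher test with 27 per arm gives 84.2%, so the claim is met. That analysis does not use the fallback.

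**3. What the switch changes.**

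| | Planned model | Fallback |
|---|---|---|
| Baseline | covariate, effect varies by visit | none stated; score or change not specified |
| Missing visits | missing at random, all visits used | observed data at that visit only |
| Early-termination score | used as next visit | not stated |

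**4. Size, model A (PASI points).** The documents give no SD, correlation or dropout mechanism for the scores. Assumed: SD of change about baseline 6 points, within-patient correlation 0.6, baseline slope -0.4, true Week 12 difference 0 or -4, and poor responders at Week 4 leaving afterwards. There were 1,500 trials per scenario. The Wilcoxon test is on observed change, with the Hodges-Lehmann shift as its estimate. The mixed model has compound symmetry with week-by-baseline and week-by-treatment terms. Negative bias favours the drug.

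| Dropout, placebo / drug | True effect | Wilcoxon bias | Wilcoxon rejects | Model bias | Model rejects |
|---|---|---|---|---|---|
| 10% / 10% | 0 | +0.04 | 10.5% | +0.01 | 10.3% |
| 5% / 20% | 0 | -0.76 | 20.9% | -0.03 | 10.9% |
| 20% / 5% | 0 | +0.75 | 5.3% | +0.05 | 8.9% |
| none | -4 | +0.03 | 82.8% | +0.01 | 88.8% |
| 10% / 10% | -4 | +0.05 | 78.0% | +0.03 | 85.9% |
| 20% / 5% | -4 | +0.72 | 67.6% | -0.01 | 86.5% |

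Monte Carlo standard error near 10% is √(0.1 × 0.9 / 1,500) = 0.8 percentage points. Counting early-termination scores as Week 8 leaves the result much the same: 20.1% rejections at 5% / 20% with no effect, and 64.6% power at 20% / 5%. These patients left after Week 4, so the rule fills Week 8 and not Week 12.

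**5. Size, model B (percentage improvement).** Assumed: baseline PASI = 12 + gamma(1.3, scale 6.5); mean Week 12 improvement 25% in both arms, or 25% versus 45%; SD 30 points; Week 8 to Week 12 correlation 0.8; leaving weighted by exp(-k × improvement). With k = 6 the weight changes by exp(6 × 0.30) = 6.0-fold per SD (strong selection). With k = 2 it changes by exp(2 × 0.30) = 1.8-fold (milder). Ranges cover the Wilcoxon test on score and on change. Without dropout its power is about 75-82%.

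| Leavers | Rejects, no effect, 5% placebo / 20% drug | Power, 20% placebo / 5% drug |
|---|---|---|
| After Week 4, strong selection | about 17-19% | about 60-67% |
| After Week 4, milder selection | about 13-14% | up to about 71% |
| After Week 8, strong, score at leaving used as Week 12 | about 7-8% | about 78-84% |
| After Week 8, strong, leavers excluded at Week 12 | about 19-24% | about 58-64% |

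With equal 10% dropout and no effect, rejection was about 11-12%.

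**The case against.** The strongest objection is the early-termination rule. Protocol section 2, footnote b, has early leavers complete all end-of-study activities, which include PASI and sPGA, and SAP 5.3 moves those scores to the next visit. A patient leaving after Week 8 then has a Week 12 value. If that carries into the fallback, the inflation for such patients goes and the test turns slightly conservative. This stands, with two limits. SAP 5.3 attaches the rule to the mixed model and does not repeat it for the Wilcoxon test. It also cannot supply a Week 12 value for someone who leaves after Week 4.

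A reader might infer a false-positive rate of 19-24%, or a power loss of about 18-23 points, as the general cost. The documents do not support that: for post-Week-8 leavers, figures of that size need strong selection and early-termination scores left unused.

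A reader might also infer that the fallback contradicts SAP 2.10. That section asks for adjustment only where possible, and a rank-sum test has no covariate term. Testing change scores would use baseline in part.

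A third tempting inference is that the trigger is likely to be met for PASI. Truncation of baseline at 12 does not by itself make residuals non-Normal once baseline is in the model. The inference is fairer for sPGA, an ordinal score from 0 to 5.

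Finally, the planning assumptions are equal 10% dropout and withdrawal unrelated to effect, and there the fallback does little harm. That is correct, but an assumption made for sample size does not protect the analysis if it fails.

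**Conclusion.** The point holds as a minor one that is cheap to improve. It is confined to the exploratory continuous PASI and sPGA comparisons. PASI 75 and PASI 90 use non-responder imputation and do not depend on this sentence. Nor do the documents say that the fallback will decide dose.

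Within that scope, a judgement about shape or covariance fit changes which patients are compared. If dropout is both response-related and unequal, the Week 12 Wilcoxon test can err either way. For leavers after Week 4 it rejects about 13-19% instead of 10% with no true effect (5% placebo, 20% drug), and power falls from about 75-82% to about 60-71% (20% placebo, 5% drug). These are the model B figures; model A put the first at 20-21% and the second at 65-68%.

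The sizes rest on assumed SD, correlation, effect and selection strength. The possibility of error in either direction does not depend on any one of them. Dropout in the simulations was missing at random, so they do not show how the mixed model would behave otherwise.

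**What to change.** Replace the closing sentence of SAP 5.3 with text to this effect:

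- If model residuals are clearly non-Normal (state how this is judged), fit the same repeated-measures model, with baseline and all visits, to a transformed score such as log(PASI+1).
- If the planned covariance structure does not fit, use a simpler one named in advance.
- Where a rank method is still needed, for example for sPGA, impute missing scores multiply under missing at random from baseline and earlier visits. Then compare each dose with placebo by baseline-adjusted rank ANCOVA.
- Apply the early-termination rule to these fallback analyses as well.
- Keep the observed-data Wilcoxon test as supplementary, and say whether it uses the score or the change.

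The cost is SAP wording and a little more programming, with no new data and no protocol amendment. The downside is interpretive: effects would be on a ratio or rank scale and not in score points.
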